A Pilot Study to Assess the Compliance and Impact on Weight of Kurbo, a Pediatric Centered Weight Loss App
Clinical Trials ID NCT02880254
Outcomes

Compliance: The compliance measure from our known standard (MIGHTY program) is showing up for a visit (e.g. attendance). As comparable measures, we will define compliance with Kurbo app to be daily use for tracking food intake, exercise, accessing the app features (games, badges). Surveys will have specific questions such as: "Over the last month, how many days per week do you usually use Kurbo to track food?" A summary compliance score will be calculated as follows: we expect subjects to use Kurbo to track food daily (7 days per week). Over the 3 follow-up study visits, if a subject responds to the above question with a 7, 5 and 6, we will take the average of this and divide it by the expected. In the above example: $18/3 = 6$ and $6 / 7 = 85.7\%$ compliant. Expected compliance for using Kurbo to track exercise = 7 days. There is no expected compliance for the use of games and obtaining badges.

Compliance with the PHC will be assessed based on the subjects' ability to have these meetings at least once a week. In order to collect this information we will ask "Over the last month, how many total meetings have you had with your personal health coach?" Compliance will be assessed in the same way as defined above with the expected compliance of 4 times in the last month. Use of the coaching feature will be defined as a complete phone or video conference. We will also assess the number of times they needed to reschedule these PHC visits.

BMI-z score: This is standard of care data that is recorded in PEDRO. The research coordinator will gather relevant BMI-z score data from PEDRO and enter it into REDCap for all study visits.

Covariates: We will collect the following from the EMR (age (yr, mo), height (cm), weight (kg), insurance category (private vs public), sex, race, and ethnicity). We will also ask subjects what their current grade level is.

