To assess our hypotheses we will utilize one-sample tests with a one-sided alpha of 0.025. One-sided tests will be used as we are only interested in whether the use of this app results in better outcomes than usual care. Compliance will utilize a binomial probability test to assess compliance (calculated over 3 months) against our known compliance of 50%. BMI-z score change (absolute change from baseline to 3 months) will utilize a one-sample t-test to assess observed BMI-z score change at 3 months against our estimated change of a 1% decrease. We will present our findings graphically, along with point estimates and one-sided 97.5% confidence intervals.

Assuming we find improved compliance and BMI-z scores, we will also estimate compliance and BMI-z score differences between Kurbo and Kurbo + PHC. Estimates will be generated using direct observation as well as prediction through modeling (e.g. GEE, linear mixed models). As data will be collected monthly, we will also describe changes over time and any possible dose-response effects. We will also evaluate possible differences in effects based on age category stratification (10-14 yrs and 15-17 yrs). We will present our findings graphically, along with 95% confidence intervals. These results may be used to inform study design and power calculations for a future study assessing differences between Kurbo and Kurbo + PHC as well as changes in obesity-related comorbidities.

Power and Sample Size: Studies in pediatric and adult weight management trials indicate that the attrition rate is poor (4, 6, 8) as well as unpublished data from our pediatric weight management spin off program, MIGHTY, indicate that 6 month compliance (attendance) is close to 50% and 6 month change in BMI-z scores is approximately a 2% decrease with a change standard deviation (SD) of 0.12. As described in our data analysis section, we will estimate compliance to be 50% and BMI-z decrease 1%. We will keep the same SD of 0.12. Sample size calculations assume a one-sided alpha of 0.025, and power of 0.80.

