In regards to compliance, we feel that to be of clinical importance we would want to observe close to 75% compliance with the Kurbo app and/or Kurbo + PHC. With a sample of 30 subjects in each Kurbo group (60 total), we would be able to conduct a one-sided, one-sample test against 50% compliance if we observe at least 75% compliance in our study groups (a 25% improvement in compliance). Larger samples would be required to test a smaller effect size (e.g. nearly 50 subjects per group would be required to test 70% compliance against 50%) and with the same sample size power would drop to 0.59 to test a 20% difference.

In regards to BMI-z score change, we feel that to be clinically relevant we would want to observe at least a 5% decrease (BMI-z score at baseline=2.267 vs. 3 months=2.154) in BMI-z score over a 3 month period

with the Kurbo app and/or Kurbo + PHC. With a sample of 12 subjects in each group, we would be able to conduct a one-sided, one-sample t-test against a 1% decrease assuming a standard deviation of 0.12 if we observe at least a 5% decrease in BMI-z score in our study groups. Effect sizes greater than the 4% difference described above will be picked up by this sample size. However, in the case that we have underestimated the SD, the upper limit of the 95% confidence interval is 0.14. With this SD we would need 19 subjects to detect this same effect.

If we progress to a comparison between Kurbo vs. Kurbo + PHC, we will utilize a repeated measures model such as GEE or linear mixed models. As we have no preliminary estimates of variability or correlation over time, we have estimated the sample required for a medium effect size of 0.50 (Cohen's d, calculated as the difference between means divided by the pooled standard deviation) assuming a two-sided alpha of 0.05, power of 0.80 and 4 repeated measures with a correlation of 0.3. In this case, we would need to sample balanced groups of approximately 28 each. If the correlation increases (e.g. 0.5 or 0.7) power will increase.

Based on the above information, in addition to adding ~20% for possible study withdrawal, we wish to recruit a total of 35 subjects in each Kurbo group for a total sample size of 70 subjects. This sample size should allow us to assess clinically relevant outcomes with sufficient power.

A Pilot Study to Assess the Compliance and Impact on Weight of Kurbo, a Pediatric Centered Weight

Loss App

Clinical Trials ID NCT02880254

Risks and Benefits

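### The primary compliance test needs a yes/no result per subject, but the plan defines only a percentage score and gives no cut-off; the 50% it is tested against is MIGHTY visit attendance, not app use

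*Combined protocol and SAP*

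**What the plan says.** All places are in the combined protocol and SAP.

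- **Outcomes, Compliance.** "A summary compliance score will be calculated as follows: we expect subjects to use Kurbo to track food daily (7 days per week"). The reported days are averaged over the three follow-up visits and divided by 7. The worked example (7, 5, 6) gives 18/3 = 6 and 6/7 = 85.7% for that one subject. For exercise: "Expected compliance for using Kurbo to track exercise = 7 days". For coach meetings: "Compliance will be assessed in the same way as defined above with the expected compliance of 4 times in the last month". No target is set for games and badges.
- **Data Analysis.** "Compliance will utilize a binomial probability test to assess compliance (calculated over 3 months) against our known compliance of 50" percent, with a one-sided alpha of 0.025.
- **Power and Sample Size.** With 30 per group the sponsor expects to "conduct a one-sided, one-sample test against 50% compliance if we observe at least 75% compliance in our study groups". It adds that "nearly 50 subjects per group would be required to test 70% compliance against 50" percent, and that power at 30 subjects falls to 0.59 for that smaller effect.
- **Source of the 50%.** "The compliance measure from our known standard (MIGHTY program) is showing up for a visit (e.g. attendance"). The power section again labels the figure as six-month attendance. Data Analysis attributes it to the usual care group and carries it to three months unchanged.
- **Primary aim.** The hypothesis is that compliance with the app, and with the app plus coach, exceeds the known compliance of the standard of care group.

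**The concern.** The endpoint and the test do not fit together. A percentage per subject cannot enter a binomial test until each subject is classed as compliant or not, and the plan gives no rule for doing so. The 75% in the power section does not supply one, because it is the level hoped for across a study group.

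This is the primary aim. Until the rule is fixed, the same app use can pass or fail depending on a choice the plan leaves open.

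Two further gaps affect the same test. The plan does not say what part the exercise and coach-meeting scores play in it. And the null value of 50% describes a different behaviour (attending MIGHTY visits), so rejecting it does not answer the hypothesis as worded.

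**Working it through.** **1. Reproduce the plan's sample size.** Inputs from Data Analysis and Power and Sample Size: p0 = 0.50, one-sided alpha 0.025, target power 0.80. Exact binomial: find the smallest k with P(X ≥ k | n, 0.5) ≤ 0.025; power is P(X ≥ k | n, p1).

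| n | k | actual alpha | power at 75% | power at 70% | plan states |
|---|---|---|---|---|---|
| 30 | 21 | 0.0214 | 0.803 | 0.589 | 0.80; 0.59 |
| 49 | 32 | 0.0222 | – | 0.810 | nearly 50 |

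49 is the smallest n that reaches 0.80 at 70% (n = 48 gives 0.749). All three stated figures reproduce with one yes/no result per subject.

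**2. Effect of the missing cut-off.** The plan gives no score distribution, so this is an illustration with assumed beta scores. For cut-off c, the share compliant is P(score ≥ c) and the chance of rejecting is P(X ≥ 21 | 30, share).

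True mean score 75%:

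| SD | c = 50% | c = 60% | c = 75% |
|---|---|---|---|
| 0.20 | 0.996 | 0.89 | 0.13 |
| 0.25 | 0.97 | 0.80 | 0.20 |
| 0.30 | 0.91 | 0.74 | 0.32 |

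For SD 0.25 the shares are 0.818, 0.748 and 0.609. With a true mean of 50% and SD 0.25, a 40% cut-off makes 0.626 of subjects compliant and rejects with probability 0.26. A 50% cut-off rejects with probability 0.02.

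**3. Would pooling days as binomial trials avoid the cut-off?** Three surveys of 7 days give 21 reported days per subject and 630 per arm, with rejection at 341 or more. Days within a subject are correlated. At a true mean of 50%, the standard deviation of the total is √(630 × 0.25) = 12.55, multiplied by √(1 + 20·SD²/0.25), where SD is the assumed between-subject SD.

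- SD 0.15: the multiplier is √2.8; (340.5 − 315)/(12.55 × 1.673) = 1.21, an upper tail of about 0.11.
- SD 0.30: the multiplier is √8.2; (340.5 − 315)/(12.55 × 2.864) = 0.71, an upper tail of about 0.24.

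Simulation agrees: about 0.11 to 0.24, against 0.025 planned.

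**4. Power if the score stays continuous.** One-sample t-test of the mean against 0.50, n = 30, noncentrality (0.75 − 0.50)/SD × √30. Power is 0.97 at SD 0.35 (0.94 simulated with beta scores). The largest SD possible for a 0–1 score with mean 0.75 is √(0.75 × 0.25) = 0.433, where the noncentral t gives 0.86. That limit is approximate: every score is then 0 or 1. With 21 of 30, t = 0.2/0.0851 = 2.35, which exceeds 2.045; with 20 of 30, t = 0.1667/0.0875 = 1.90, which does not. The t-test then rejects exactly when the binomial does, with power 0.803.

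**5. Subjects with no survey.** Surveys are completed at clinic visits (Randomization, Allocation and Blinding), and the plan allows for "adding ~20% for possible study withdrawal". As an upper assumption, take 7 of 35 unscored and overall compliance of 50%. With compliant share q among the unscored, the rate among the 28 scored is (0.5 − 0.2q)/0.8, and the binomial rejects at 20 or more of 28.

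- q = 0: rate 0.625, rejection 0.22.
- q = 0.25: rate 0.5625, rejection 0.075.
- q = 0.5: rate 0.50, rejection 0.018, so no inflation.

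For the t-test on 28 scored subjects with an overall mean of 50%, unscored subjects who are all non-users give a scored mean of 0.625 and rejection of about 0.44 to 0.89 (SD 0.35 down to 0.20). If the unscored average 25%, it is about 0.15 to 0.36.

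**The case against.** **The sample size is correct.** This stands. A reader might infer that 30 per group is an error, and the documents do not support that: 30, nearly 50 and 0.59 all reproduce. What the match shows is that the sizing relies on a yes/no definition that the plan never gives.

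**Food tracking is plainly the score meant.** This largely stands. The summary score and its worked example use food tracking only, so that is the natural reading. The place of the exercise and coach-meeting scores is still not stated, and the primary aim explicitly includes the coach.

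**The benchmark mismatch is disclosed.** This stands. The plan says the 50% is attendance and calls the measures comparable, so a reader would be wrong to infer concealment. But comparability is asserted without support, and disclosure does not make attendance and daily tracking the same quantity. This limits the conclusion; it does not stop the test from being run.

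**It is a pilot.** The plan nevertheless sets an alpha, a power and a directional hypothesis for this outcome.

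**A t-test is a matter of taste.** This stands in part. Fixing a cut-off changes the plan least, and the t-test on scored subjects is more exposed to selection than the binomial (step 5). Neither option is clearly better.

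**The sizes are assumed.** True: score distributions and unscored rates are not in the documents. The pattern across cut-offs holds for SDs of 0.20 to 0.30.

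**Conclusion.** The primary compliance test is wrong as written and must be fixed before analysis. It cannot be run on the defined endpoint without an unstated cut-off, and that cut-off can move the chance of success from 0.97 to 0.20 for the same mean score of 75% (assumed beta scores, SD 0.25, 30 subjects). Pooling days is no way out, since it would raise the one-sided error to about 0.11 to 0.24 (assumed between-subject SD 0.15 to 0.30).

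The benchmark is a separate point of interpretation: rejecting 50% would show app use above a chosen level, not better compliance than standard care.

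Two stronger readings go too far. One is that missing surveys necessarily favour the app: they do so only if the unscored comply less than the others, and the plan's 20% is withdrawal. A subject who withdraws after one survey still has a score. The other is that the sponsor intends to choose the cut-off after seeing the data; the documents are silent on this.

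**What to change.** 1. **Data Analysis.** Choose one of two equal options before any data are seen. (i) Test the mean food-tracking score in each arm against 50% with a one-sided one-sample t-test at alpha 0.025, and restate power. (ii) Keep the binomial test and its sizing, and state the food-tracking score at which a subject counts as compliant. Option (ii) changes the plan least.
2. **Exercise and coach scores.** Analyse exercise scores in both arms, and coach-meeting scores in the Kurbo + PHC arm, separately. State whether the coach score is also tested, since the primary aim covers the coach.
3. **Benchmark.** State that 50% is an attendance figure used as a chosen target, and reword the primary hypothesis and the planned conclusion to match. A new test of attendance against MIGHTY is not required.
4. **Missing surveys.** Average the surveys a subject has. As a sensitivity analysis, count randomised subjects with no survey at all as score 0 (or non-compliant), and report whether the conclusion changes. Do not score visits that were never scheduled as 0: visits fall every 4 to 6 weeks, and Follow-Up accepts fewer data points when they are not four-weekly.

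**Cost.** Text changes and, under (i), a restated power calculation; no new data. The remaining weakness is that leaving out unscored subjects can favour the app under either test, more so under the t-test (about 0.44 to 0.89 against 0.22 in the extreme case of step 5). The sensitivity analysis is there to expose this.

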Study Timeline: We plan to recruit 70 subjects within the first 6 months of protocol acceptance. With nearly 22 new patients a week we do not anticipate that recruitment will take longer than 2 months, however we will leave our recruitment window open for 6 months at which time we will close recruitment, even if we have not accrued 70 subjects. As the Kurbo intervention is 3 months in duration, we expect the full implementation of this study to last approximately 9 months. Data analysis will be initiated by the EBRC at the completion of data collection. We anticipate analysis to take 3 months.

Prior Studies and Feasibility: As this is a pilot study, no preliminary studies have been conducted in support of this study. We anticipate timely recruitment given the high volume of new patients in our weight management clinic. In order to establish feasibility for a larger study, we will measure participant compliance and other feasibility measures with this pilot study.

The Principal Investigator has experience in conducting retrospective trials, drug treatment trials, prospective and randomized controlled trials during her time at Baystate as well as during her fellowship. Other members of the team, including the research coordinator and other providers, have also had some research experience in retrospective and prospective randomized controlled trials.

Data Analysis: We wish to evaluate two outcomes (compliance and BMI-z score change) among two groups (Kurbo and Kurbo + PHC). To do this we will use two single arm studies, where subjects will be randomized into either group, however each will be compared to a known standard. In this case, the known standards (based on existing data from our usual care group) are based on a 6-month compliance rate of 50% and a BMI-z score decrease near 2% (BMI-z score at baseline=2.27 vs. 6 months=2.22). To adapt these to a 3-month intervention, we feel that compliance at 3 months will remain the same (50%) and BMI-z change will be around 1% (BMI-z score at baseline=2.27 vs. 3 months=2.25).

Upon completion of the study, data will be inspected for outliers and logic checks will be conducted. Initial results will include means, standard deviations, medians and ranges for continuous measures and frequencies and percentages for categorical measures. Graphical representations will be utilized as needed.

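### As written, the BMI-z test can use only subjects with a 3-month value although about 20% withdrawal is expected; if withdrawers do worse, its false-positive rate may exceed 0.025

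*Combined protocol and SAP*

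**What the plan says.** All references are to the combined protocol and SAP.

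- **Test (Data Analysis).** "To assess our hypotheses we will utilize one-sample tests with a one-sided alpha of 0.025". For the secondary outcome, "BMI-z score change (absolute change from baseline to 3 months) will utilize a one-sample t-test to assess observed BMI-z score change at 3 months"; the comparator is an assumed 1% decrease.
- **Benchmark (Data Analysis).** "BMI-z change will be around 1% (BMI-z score at baseline=2.27 vs. 3 months=2.25". It is adapted from the 6-month result of MIGHTY, the reference programme, where attendance was close to 50%.
- **Expected loss (Power and Sample Size).** The target of 35 per group is reached "in addition to adding ~20% for possible study withdrawal". The same section describes attrition in weight management trials as poor.
- **Data collected (Follow-Up; Outcomes).** Children are seen every 4-6 weeks as standard care, and BMI-z for study visits is taken from the routine clinic record.
- **Use of the repeated values (Data Analysis).** "As data will be collected monthly, we will also describe changes over time". GEE and linear mixed models are named only for the Kurbo versus Kurbo + PHC estimates, which follow only if improvement is found.

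No section defines an analysis population, an imputation rule or a missing-data sensitivity analysis for BMI-z.

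**The concern.** A one-sample t-test on change needs both a baseline and a 3-month value. With withdrawal expected and no other handling given, the tested quantity becomes the mean change among those who reach the final visit, not among those enrolled.

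This design is more exposed than a controlled comparison. In a two-arm test, similar selective loss in both arms would partly cancel. Here any shift in the completers' mean enters the test in full. If children who stop attending have lost less, the shift is towards success. A positive result would open the comparison between the two Kurbo arms and, under Significance and Innovation, support a larger study.

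**Working it through.** **Inputs from the documents**
- One-sided alpha 0.025; 35 per group; about 20% withdrawal.
- SD of change: "We will keep the same SD of 0.12". If that is too low, "the upper limit of the 95% confidence interval is 0.14".
- Null: 1% of 2.27 = 0.0227 decrease (0.02 from the rounded 2.27 to 2.25).
- Clinically relevant effect: "at least a 5% decrease (BMI-z score at baseline=2.267 vs. 3 months=2.154". The 4-point difference from the null is 0.04 × 2.267 = 0.0907.

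**The plan's own figure.** 28 / (1 − 0.20) = 35, so the target matches the 28 per group quoted for the between-arm model, with 28 left after 20% loss. Against the 30 per group needed for compliance, 35 allows a loss of 5/35 = 14.3%. Both cases are shown below.

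**Power is not the problem.** With 28 analysed and a difference of 0.0907, the exact one-sample t-test has power 0.97 at SD 0.12 and 0.91 at SD 0.14. Recruiting more children would not help.

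**Error of the completers' test.** Suppose the mean change of all enrolled equals the null, so that any rejection is false. Let w be the fraction lost, n the number analysed, and D the amount by which withdrawers' mean change is worse than completers'. D is an assumption.

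- Shift of the completers' mean: s = w × D.
- Noncentrality: s × √n / SD.
- Error: probability that a noncentral t with n − 1 degrees of freedom exceeds its 0.975 critical value (2.052 for n = 28).

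If withdrawers have zero change, the completers' mean must be −0.0227 / 0.80 = −0.0284. Then D = 0.0284 and s = 0.0057. The standard error is 0.12 / √28 = 0.0227, the noncentrality is 0.25, and the error is 0.043.

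| Assumption about withdrawers | Shift, 20% lost (n = 28) | Error | Error, 14.3% lost (n = 30) |
|---|---|---|---|
| Better by 0.05 | −0.010 | 0.0085 | 0.011 |
| No difference | 0 | 0.025 | 0.025 |
| Zero change | 0.0057 | 0.043 | 0.037 |
| Worse by 0.05 | 0.010 | 0.063 | 0.050 |
| Worse by 0.0907 | 0.018 | 0.117 | 0.083 |

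With SD 0.14 and n = 28, the last two rows become 0.055 and 0.097.

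**Cross-check by simulation** (40,000 runs, 35 enrolled, 20% lost, SD 0.12, a latent correlation between worse change and withdrawal). The error was 0.023 at correlation 0, 0.054 at 0.2 and 0.079 at 0.3. It was 0.006 at −0.3. The pattern is the same.

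**The case against.** The strongest reply has five parts.

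1. **Inflation is conditional.** A reader might infer that false positives do rise. The documents do not support this: nothing in them says that withdrawers do worse, and the table shows 0.025 under unrelated loss and less than that under the opposite pattern. This stands; "may" is the right word.
2. **The wording is not an exclusion rule.** In the quoted sentence the observed change is contrasted with the estimated benchmark, and the test could be run on imputed or retrieved values. This also stands. But a subject with no final value has no change score, and no other handling is given, so the completers' analysis is what the text yields.
3. **The benchmark may carry the same selection.** If the MIGHTY change came from attenders only, a completers' test is nearer to like with like, and testing an all-enrolled estimate against it could work against the app. The documents do not say. This is a reason to state the benchmark's source, not to leave the method open.
4. **Loss may be smaller than feared.** A reader might also apply the 50% attendance figure as the loss rate. It is a 6-month figure from a different, intensive programme, used as a compliance standard. The only loss rate stated for this study is about 20%, and that is study withdrawal; a child who leaves the app may still have a clinic BMI-z.
5. **A mixed model is not a full cure.** It can correct loss that depends on earlier recorded BMI-z. It cannot correct loss that depends on unseen values, and a subject with only a baseline adds almost nothing. If withdrawers have zero change whatever was observed before, most of the shift remains. This stands, and is why a sensitivity result is needed as well.

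**Conclusion.** The concern holds in a conditional form. The BMI-z test as written is a completers' test against a fixed benchmark, in a study that expects about 20% withdrawal and gives no missing-data method, although it collects data and names a model that would do better.

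At that loss rate the nominal 0.025 may become about 0.043 if withdrawers show no change, and about 0.06 to 0.12 if they do worse by 0.05 to 0.09. These figures assume SD 0.12, 35 enrolled, 28 analysed and a full-cohort mean equal to the null. The zero-change shift of 0.0057 is small beside the targeted 0.09; it matters for the error rate, and much less for whether a 5% decrease would be detected. BMI-z is the secondary aim of a pilot, so the change is worth making but does not call the study into question.

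**What to change.** - **Main analysis.** Estimate each arm's month-3 mean BMI-z change from a linear mixed model using all enrolled subjects and all available monthly values, and test that estimate against the benchmark at one-sided 0.025. Follow-Up warns that some interim values may be absent, so the plan should say how visits of uneven timing enter the model.
- **Data retrieval.** State that BMI-z will be taken from the routine clinic record for subjects who stop using the app but still attend.
- **Sensitivity result.** Report beside it the result with zero change for subjects without a 3-month value. Read it mainly for the move in the point estimate, since filling in a constant understates the spread.
- **Benchmark.** State whether the reference change came from all MIGHTY subjects or attenders only, and interpret the test accordingly.

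The cost is a little more analysis, with data and models already planned, and an estimate that may be less favourable. The sample size need not change.
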